7.3.4 Telephone Communication

Subjects will be instructed to call the clinic should they be experiencing any self-perceived adverse events, or if they have any study-related questions. All telephone information will be documented.

7.3.5. Products Description (How Administered)

The product is an all-natural patented 20 mM sodium pyruvate in 0.9% sodium chloride nasal spray solution with 0.02% benzalkonium chloride as a preservative. The plastic bottle contains 30 mL. It is non-steroidal. Patients will forcibly expel air from their lungs and then will administer three sprays per nostril while inhaling strongly so that the drug is transported through the nose and into the lungs. The drug is to be administered three times per day (morning, mid-day, and evening). The product comes with instructions for administration (three sprays per nostril).

7.4 Concomitant Therapy

No concomitant therapy is prescribed for this study, but the subjects may continue to use their normal therapy as long as they list it as a current medication. The Principal Investigator may prescribe "rescue medication" should it be required by any of the patients. Patients may continue taking nutritional supplements. safety. Subjects may not use any of the following during the trial or for one week before enrollment in the trial: all intranasal medications or lavages, antihistamines, steroids or anti-inflammatory medications of any kind. Subjects also may not currently be taking any antiviral or antibiotic medications.

8.0. The Method For Determining The Dose(S) To Be Administered, The Planned Maximum Dosage, And The Duration Of Individual Patient Exposure To The Drug.

This is a constant dose study. The amount of delivered sodium pyruvate was determined in clinical trials to be three sprays of 20 mM sodium pyruvate in 0.9% sodium chloride solution per nostril, and this is repeated 3x per day (morning, midday, and evening). The dose was determined by evaluating the data from both animal and human studies (cited above).

9.0. A Description Of The Observations And Measurements To Be Made To Fulfill The Objectives Of The Study.

Observations for safety will include a pregnancy test for women of child-bearing age, blood oximetry, and vital signs.

Observations for efficacy will include evaluation of sore throat, congestion, erythema, the number of daily coughs, and flu-like symptoms. Perceived adverse events will be monitored.

Premature Withdrawal

The patients can withdraw from the study at any time, and for any reason. All data collected from these patients will be analyzed. Reasons for withdrawal will be recorded to ensure that it was not due to an adverse event.

Test	Pre-study visit	Day 0 Visit 1	Day 2	Day 4	Day 6	Day 8, etc.
Clinic Visit or telehealth check		+	+	+	+	+
Informed Consent	+					
Medical History	+	+				
Physical Exam/	+					
Observe Administer Drug		+	+			
Pregnancy Test for Females	+					
Concurrent Medications Reviewed	+	+	+	+	+	+
Symptom Data Logbook (Clin. App.)		+	+	+	+	+
Adverse Events Reviewed		+	+	+	+	+
Nasal Swab for virus titer		+	+	+	+	+

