1.1.2 Background and Product Description

N115 is a sodium-pyruvate-based inhalation drug. It has been administered via several routes including intravenous, topical administration for hyperkeratotic disorders, and as an enteral supplementation since it is considered GRAS (Generally Regarded as Safe) by the FDA. Sodium pyruvate is used in many products including (Neosporin, Lubriderm, vaginal products, Viva Eye Drops, Ringers Solution, human IV solutions, and solutions to store red blood cells by the Red Cross, and to store human organs for transplant). Sodium pyruvate has been shown to protect neurons, lungs, hearts, muscles, cerebral metabolism, embryos, eyes, kidneys, cellular DNA and membranes from oxygen radical damage. Other approved uses in patients with a variety of medical disorders include Friedreich's disorder; and it is used as a therapeutic solution in open heart surgery, kidney surgery, and eye surgery.

Six different nasal spray formula combinations were tested for safety and efficacy in a series of studies with subjects who normally use nasal sprays. The sodium pyruvate concentrations were 5mM, 10mM, 20mM and 40mM. The sodium pyruvate was delivered in sterile sodium chloride solutions of either 0.45% or 0.90%. All formulas reduced inflammation in the nasal cavities and otherwise improved the nasal cellular morphology. There weren't any adverse events observed.

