- Covid-19 positive individuals will receive the nasal spray that will be used three times per day. This spray will be placebo control (15 patients, 0.9% sodium chloride with 0.02% benzalkonium chloride) or N115 treatment (15 patients, 20mM sodium pyruvate in 0.9% sodium chloride with 0.02% benzalkonium chloride). Study staff and subjects will be blinded.
- 3. Patients will return for testing again every other day to determine how fast the nasal spray reduces the viral load and infection, compared to the viral loads and infection on Day Zero, historical baselines, and placebo.

EmphyCorp Rx N115 Non-Steroidal Nasal Spray increases nasal nitric oxide and has the potential of reducing the rate and spread of COVID-19 among healthy individuals, diabetics, and others. Nasal steroids and other OTC nasal treatments shut down the synthesis of nasal nitric oxide which increases the rate of infections. This would indicate that the use of EmphyCorp's Rx N115 Nasal Spray by healthy individuals including Adults, Children, Pregnant Women, and Diabetics that are currently infected with COVID-19 without other underlying health conditions, could reduce the rate, duration and spread of infection.

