5.2. Institutional Review Board

5.3 Study Objectives

Primary Objective

- a. The primary objective is to evaluate the effects of inhaled nasal sodium pyruvate (N115) in patients with confirmed COVID-19 or flu infections by determining changes in the duration of an active infection by PCR from nasal.
 Secondary Objective
- **a.** The second objective is to evaluate the ability of the inhaled nasal sodium pyruvate therapy in subjects with COVID-19 or flu infections to improve symptoms by the use of a patient diary and by collecting periodic vital signs, especially body temperature, blood pressure and pulse/Ox.

5.4. Study Design Overview

Individuals that are symptomatic for COVID19/influenza will initially be tested by Dynamic DNA Labs or Trinity Healthcare (Screening Visit). If positive for COVID19/influenza, patient will then be solicited for participation in the trial within 24 hours. After signing Informed Consent, women of child-bearing age will provide a urine sample to test for pregnancy. They will be randomly assigned to either the placebo or drug groups in a double blinded fashion and be given a data logbook, or clinical app for their phone, in which they will record the number of coughs and other flu-like symptoms they experience each day. Patients will be contacted by phone and/or sent reminders through a clinical phone app every two days to review symptoms and protocol compliance and patients will be tested via nasal swab every other day. This will continue every other day until the subject tests negative for COVID-19/ influenza (which is

defined as a 2-Log reduction in virus titer or less than 1000 copies of viral RNA) or 14 days, whichever comes first. Personnel collecting swabs will wear N95 mask and face shield, disposable examination gloves and disposable gown while collecting nasal swabs from patients. Samples will be collected outdoors, weather permitting, or in a well ventilated room in inclement weather.

6.0. The criteria for patient selection and for exclusion of patients, and an estimate of the number of patients to be studied.

6.1. Subject Selection

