6.1.1 Number of Patients to be Studied

Fifteen patients with confirmed COVID-19 infection will be enrolled in the trial in the drug group and fifteen with confirmed COVID-19 infection will be enrolled in the trial in the placebo group. An additional fifteen patients with confirmed influenza infection will be enrolled in the trial in the drug group and fifteen with confirmed influenza infection will be enrolled in the trial in the placebo group. Efforts will be made to include women and minorities. The study will be double blinded to subjects and study investigators.

6.2. Inclusion Criteria

- **6.2.1.** Individuals with a confirmed COVID-19/influenza viral infection, as determined by a qualified laboratory test. A nasal swab or saliva test analyzed by qPCR for COVID19 or rapid flu test from nasal swab for influenza.
- **6.2.2.** Individuals who agree to abstain from sexual intercourse, or agree to use condoms or vaginal diaphragms or other devices designed to prevent contraception, during the entire course of the study

6.3. Exclusion Criteria

- **6.3.1.** Viral infections other than COVID-19 or influenza.
- **6.3.2.** Clinically significant cardiac disease including uncontrolled congestive heart failure and unstable angina
- 6.3.3. Pregnancy
- **6.3.4.** Females of child bearing potential age not on adequate contraception or lactating
- **6.3.5.** Subjects receiving systemic corticosteroid treatment within one month of Screening Visit
- 6.3.6. Subjects Less than 18 years of age
- **6.3.7.** Hospitalization within last 6 months due to acute exacerbation of airway disease
- **6.3.8.** Subjects with a clinically significant abnormal chest x-ray within past 12 months
- **6.3.9.** Medication changes within one month of study entry
- **6.3.10.** Subjects who have participated in another investigation drug treatment study within the previous month.
- **6.3.11.** Subjects with a current history of alcohol or recreational drug abuse.
- **6.3.12.** Subjects who have taken dietary supplements containing pyruvate within 24 hours prior to the screening visit.

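### Pyruvate supplements are screened for over the 24 hours before screening, but Section 7.4 lets nutritional supplements continue during treatment with no stated exception for pyruvate

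*Combined protocol and SAP*

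**What the plan says.** Section 7.3.5 describes the study drug: "The product is an all-natural patented 20 mM sodium pyruvate in 0.9% sodium chloride nasal spray solution". The comparator is set out under Purpose and Objectives of the Studies: "This spray will be placebo control (15 patients, 0.9% sodium chloride with 0.02% benzalkonium chloride". The two sprays share saline and preservative and differ only in pyruvate.

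Three provisions bear on pyruvate from other sources:

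- **Exclusion 6.3.12** removes "Subjects who have taken dietary supplements containing pyruvate within 24 hours prior to the screening visit".
- **Section 7.4, permission:** "Patients may continue taking nutritional supplements". No type of supplement is excepted and no limit is stated.
- **Section 7.4, products barred during the trial and for the week before enrolment:** "all intranasal medications or lavages, antihistamines, steroids or anti-inflammatory medications of any kind". Antivirals and antibiotics are also barred. Neither pyruvate nor supplements appear.

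Section 1.1.2 acknowledges that pyruvate has been given "as an enteral supplementation since it is considered GRAS". The testing schedule has concurrent medications reviewed at every visit, and the diary in Section 16.0 records medication changes. Neither mentions supplements.

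**The concern.** The protocol treats supplemental pyruvate as something to keep out of the trial, but its only explicit restriction looks back from screening. Once treatment starts, the text on supplements is a general permission.

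What is at stake is the contrast between arms. If a placebo patient takes pyruvate by another route, and that route influences viral clearance or symptoms, the arms differ by less than the design intends and the estimated effect shrinks towards zero. Use in the drug arm would add exposure that the trial neither controls nor records. Because no form names supplements, the analyst might be unable to describe use by arm afterwards, let alone examine its influence.

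**Working it through.** The plan states no figure on this point, so there is none to reproduce. The check has two parts.

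**1. Timing, from the text**

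- Symptomatic people are tested at the Screening Visit. After a positive result, Section 5.4 says the "patient will then be solicited for participation in the trial within 24 hours". Consent, randomisation and first dose follow.
- The 6.3.12 window closes at the Screening Visit, before the trial is raised with the patient. It therefore works as a history question and not as an instruction.
- Swabs continue every other day until the patient tests negative "or 14 days, whichever comes first". No section restricts pyruvate supplements during this period.
- Someone who took pyruvate in the window is excluded, so most daily users are removed. The routes left open are intermittent use, a chance pause on that day, and starting or resuming after screening.

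**2. Size of the dilution**

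Inputs from the documents: 15 drug and 15 placebo patients for each virus (Section 6.1.1).

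Inputs not in the documents, and so assumed:

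- k, the number of placebo users in an arm.
- r, the effect of oral pyruvate as a fraction of the spray's effect, from 0 (inactive) to 1 (as good as the spray).
- Oral pyruvate adds nothing to the spray in the drug arm. If it added equally in both arms and use were balanced, the bias would cancel. Taking no addition gives the larger dilution.

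Formula: observed difference = true difference × (1 − r × k/15).

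For one user (k = 1):

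- r = 1: 1/15 = 6.7% dilution
- r = 0.5: 0.5/15 = 3.3%
- r = 0: none

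**Illustration in terms of power.** Section 18.2 gives no significance level, power, effect size or SD. Assume a two-sided 5% level, 80% power without contamination, and the normal approximation for two means. The standardised difference detectable with 15 per arm is (1.960 + 0.842) × √(2/15) = 1.023. Under the worst case r = 1:

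| Placebo users of 15 | Diluted difference | Power | n per arm to restore 80% |
|---|---|---|---|
| 0 | 1.023 | 80% | 15 |
| 1 | 1.023 × 14/15 = 0.955 | 74% | 18 |
| 2 | 1.023 × 13/15 = 0.887 | 68% | 20 |
| 3 | 1.023 × 12/15 = 0.818 | 61% | 24 |

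For one user: power = Φ(0.955/√(2/15) − 1.960) = Φ(0.655) = 74%. With r = 0 every row stays at 80%.

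**The case against.** The strongest reply is that the gap is narrow and its consequence unproven. Most of that stands.

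- **The permission is to continue.** A reader might infer that 7.4 gives every patient unlimited access to pyruvate. The text does not support that. It most naturally covers supplements already in use, and 6.3.12 has removed anyone who took pyruvate in the day before screening. What remains is that no limit or exception is stated.
- **The pre-screening window has a purpose.** A reader might infer that it covers a day with no bearing on the endpoint. But clearance can be met by a 2-log fall in viral RNA (Sections 5.4 and 7.3.3), and the analysis uses baseline as a covariate (Section 18.2). If supplemental pyruvate acts at all, intake just before screening could affect the starting titre.
- **Oral is not nasal.** The rationale rests largely on local effects: nasal nitric oxide and nasal congestion. Other intranasal products are already barred. No passage shows that oral pyruvate lowers nasal viral load, so the documents do not support saying that supplement use erases the difference between arms. Comparing a supplement's mass with the sprayed mass does not help: the documents give neither spray volume nor supplement dose, and the routes differ.
- **The ban on anti-inflammatory medications might cover it.** Section 3.0 presents pyruvate as reducing inflammatory agents. But that ban concerns medications, while the same paragraph permits supplements. If sites could read it either way, the text needs settling.
- **Partial safeguards exist, and dilution from placebo use cannot create a false positive.** Both are true. The medication review could pick up supplements, but nothing asks for them.

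A stray word follows the permission in 7.4, so text may have been lost there. The available wording carries no qualifier.

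**Conclusion.** The point holds as a minor inconsistency. Section 6.3.12 treats supplemental pyruvate as a reason for exclusion, and 7.4 permits supplements during treatment without carrying that restriction forward. A placebo patient may therefore take the active ingredient within the rules.

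The size is conditional. The upper bound of about 6.7% dilution per placebo user holds within one virus group of 15 per arm and requires oral pyruvate to work as well as the spray. It falls to nothing if oral pyruvate is inactive. The documents do not establish any oral effect and give no rate of supplement use. The number of users is probably small. The documents do not support a conclusion that the comparison is compromised. They support only that an avoidable source of dilution is left open and may go unrecorded.

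**What to change.** Reconcile 7.4 with 6.3.12 so that the pyruvate-supplement restriction the protocol already applies before screening is carried through to the last study swab. One clause added to the supplement sentence in 7.4 is enough.

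Add supplements by name to the concurrent-medication review already scheduled at every visit, and tabulate their use by arm.

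The cost is one clause and one line on an existing form, with no added visit or test. A few patients would forgo a pyruvate supplement for at most about 14 days. The recording should be in place before enrolment, because intake that nobody asked about is hard to reconstruct later.

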8.2 Testing Schedule-Sub-Chronic Phase of COVID-19 or flu positive patients

12.0 Safety Testing

12.1 Physical Exam

12.2.1 Nasal swab test for COVID-19 or influenza virus analyzed by qPCR.

13.0 A description of clinical procedures, laboratory tests, or other measures to be taken to monitor the effects of the drug in human subjects and to minimize risk

Tests and analyses will be conducted every other day during the study. If any aberrant values occur, the Clinical Coordinator will determine if that patient should continue the study or be removed. All aberrant values that occur during the study will be considered adverse events.

14.0. Safety Precautions Included in this Study:

The 20 mM nasal sodium pyruvate inhalation has been administered to both healthy humans and humans with lung diseases, without the occurrence of any SAE.

- First administration of nasal spray monitored via telehealth on in clinic.
- The initial nasal spray will be administered under the supervision of medical staff.

^{12.2} Efficacy Tests

• If a subject develops any adverse event during the follow-up period after study drug administration, the subject will be treated to a satisfactory resolution before being discharged from the clinic.

• Subjects will remain in contact via telehealth or in the clinic for 30 minutes after the initial inhalation of the nasal spray.

• Follow up telephone communications, as needed.

• If at any time the patient shows severe signs of disease or complications, they shall be removed from the study by the physician ([name]) and treated using proven methods for COVID19 or flu. These include, but are not limited to, antiviral drugs (Tamiflu, remdesivir, etc.), convalescent serum, oxygen and critical care. Treatment decisions will be made by [name], the patient's physician or an emergency care physician as needed. The patient may also withdraw from the study at any time, and for any reason, and seek traditional standard of care for COVID19 or flu.

• Severe signs of disease or complications include abnormal blood pressure (low or high), resting blood O₂ below 90%, apnea, fever over 103° F, altered mental state, impaired renal function, hemorrhaging or other severe symptoms.

15.0 Product Evaluation Questionnaire. This information will not be collected in the current study as it has been collected in numerous prior studies.

16.0 Daily Data Logbook:

Subjects will use this diary card or a clinical phone app to record the number of their coughs per day and flu-like symptoms, any self-perceived adverse events, and any medication changes during the study.

17.0 Urinalysis: Samples may be taken and analyzed to determine if any females of child bearing age are pregnant

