19.2. Examples of Adverse Events

- Inter-current illnesses
- Injuries
- New symptomatology (this does not include symptoms expected as a result of the subject's condition unless it is beyond what is normally expected)
- Significant laboratory abnormalities
- New abnormal physical exam findings
- Significant exacerbation of pre-existing conditions

19.3. Recording and Documentation of Adverse Events

Any adverse event (i.e., a new adverse event or an exacerbation of a pre-existing condition) with an onset date after study drug administration should be recorded as an adverse event on the Case Report Form (CRF). All adverse events must be recorded on the appropriate CRF regardless of the severity or relationship to study medication.

An adverse event or laboratory abnormality with an onset date before study drug administration is considered to be pre-existing in nature. These pre-existing events, will be noted in the CRFs.

All SAEs occurring during this study, whether observed by the physician, nurse, or reported by the patient, will be recorded on the Florida Advanced Medical Research Adverse Events form

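### Section 13.0 makes every aberrant value an adverse event, which conflicts with sections 19.2 and 19.3 for readings abnormal before dosing and for expected signs of the infection

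*Combined protocol and SAP*

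**What the plan says.** Four sections bear on what counts as an adverse event.

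- **Section 13.0**, on tests made every other day: "All aberrant values that occur during the study will be considered adverse events". The term *aberrant* has no definition, threshold or reference range.
- **Section 19.1** allows an adverse event to be either expected or unexpected.
- **Section 19.2** is a list of examples. It includes "Significant laboratory abnormalities", without defining *significant*, and "New symptomatology (this does not include symptoms expected as a result of the subject's condition unless it is beyond what is normally expected".
- **Section 19.3** ties recording to onset after study drug, and it includes worsening of a pre-existing condition. For earlier onset it says: "An adverse event or laboratory abnormality with an onset date before study drug administration is considered to be pre-existing in nature". It sets no severity floor: "All adverse events must be recorded on the appropriate CRF regardless of the severity or relationship to study medication".

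No section says which of these takes precedence. Temperature, pulse oximetry and blood pressure are taken at the pre-study visit (7.3.1) and at each two-day follow-up visit (7.3.3). They serve the secondary objective (5.3), and oximetry and vital signs are also safety observations (9.0). Follow-up stops when the patient is virus free or at 14 days (7.3.3).

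**The concern.** Everyone enrolled has symptoms of the infection under study (5.4), so abnormal readings at entry and in the first days are to be expected. If 13.0 is applied literally, each such reading is an adverse event. If 19.2 and 19.3 are applied, many may be pre-existing or part of the illness. Two members of staff following different sections would record the same patient differently.

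The number of readings also depends on when the patient tests negative, so a count under 13.0 partly measures how long the infection lasts. That could obscure events caused by the spray. It could also make a benefit on fever or viral clearance look like better tolerability. The label has consequences beyond the count: adverse events go on the CRF (19.3), are scored for attribution (19.6) and, if not serious, are reported at protocol continuation (19.5).

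**Working it through.** The documents state no expected adverse event rate and no adverse event analysis, so there is no figure to reproduce. The check is a comparison of text, followed by an illustration of scale.

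**Step 1. Apply each rule to the same reading.**

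| Reading | Under 13.0 | Under 19.1 to 19.3 | Result |
|---|---|---|---|
| Abnormal before first dose, unchanged at Day 2 | Adverse event | Pre-existing (19.3) | Conflict |
| New fever after dosing, within the usual course of the infection | Adverse event | Left out as an expected symptom (19.2), although 19.1 allows expected events | Conflict |
| New or worsened reading beyond what the infection explains | Adverse event | Adverse event | Agree |
| New abnormal value of no significance | Adverse event | Not named in 19.2, not expressly excluded; 19.3 has no severity floor | Unclear, not a contradiction |
| qPCR still positive at follow-up | Adverse event if a positive result is aberrant | Infection began before dosing | Unclear |

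The firm conflict is in the first two rows.

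**Step 2. Number of readings.** There are 3 vital-sign measures per visit (7.3.3), with visits every two days up to Day 14, and 60 patients (6.1.1: four groups of 15).

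- To Day 14: visits on Days 2, 4, 6, 8, 10, 12 and 14 make 7. Then 7 × 3 = 21 readings per patient, and 60 × 21 = 1,260 in all.
- If everyone stopped at Day 6: 3 × 3 = 9 readings per patient, and 60 × 9 = 540 in all.
- Counting the swab as a fourth value to Day 14: 7 × 4 = 28 per patient, and 60 × 28 = 1,680 in all.

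**Step 3. What 13.0 could produce.** Let p be the chance that a reading is aberrant. The documents do not give p, so a range is assumed and readings are treated as independent. The chance of at least one event per patient is 1 − (1 − p)^n. The expected number of aberrant readings is 60 × n × p.

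| p (assumed) | n = 9: chance; total | n = 21: chance; total |
|---|---|---|
| 1% | 9%; 5 | 19%; 13 |
| 5% | 37%; 27 | 66%; 63 |
| 10% | 61%; 54 | 89%; 126 |
| 20% | 87%; 108 | 99%; 252 |

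These totals count readings. One fever seen at three visits could be a single event. Some of these readings would also qualify under 19.2 and 19.3. The totals are therefore not the size of the discrepancy, which cannot be calculated while *aberrant* and *significant* are undefined.

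**Step 4. Dependence on follow-up.** Assume 30 patients per arm, p = 10% in both arms, and an average of 3 visits in one arm and 5 in the other. Aberrant readings are 30 × 3 × 3 × 0.10 = 27 against 30 × 5 × 3 × 0.10 = 45. If every patient had exactly that number of visits, the chance of at least one would be 1 − 0.9^9 = 61% against 1 − 0.9^15 = 79%. The arms differ although the rate per reading is the same.

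**The case against.** The strongest reply is that the sections are closer than they look.

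- Section 19.2 gives examples, not an exhaustive definition, and its exception concerns symptoms, whereas 13.0 concerns measured values.
- Section 13.0 speaks of values that arise during the study. That can be read as new onset, which would largely agree with 19.3.
- Recording broadly and then attributing is a legitimate approach. CTCAE grading (19.1) and the five-level attribution score (19.6) help to separate disease from spray.
- Both arms are blinded and follow the same rules, and 18.2 plans no comparison of adverse events between arms.

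Much of this stands, and it limits the point. A reader might infer that 19.2 excludes all non-significant findings. It does not: it is a list of examples, and 19.3 records events of any severity. A reader might also infer that disease-related readings will swamp the count, or that a planned safety comparison is invalid. The documents support neither, given attribution, grading and the absence of a planned comparison. Using vital signs for both efficacy and safety is not an error in itself, and a single definition would not fully separate the two roles.

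Two things do not fall away. The new-onset reading of 13.0 is possible, but the text does not say it. Fever is both a value and a symptom, so the exception in 19.2 and the rule in 13.0 meet on the same reading. Equal rules in both arms do not remove the dependence on number of visits if one arm clears virus sooner.

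**Conclusion.** The point holds in a limited form. Section 13.0 is broader than 19.2 and 19.3 and contradicts them for two kinds of reading: those abnormal before the first dose and unchanged afterwards, and those that are also expected symptoms of the infection. In symptomatic patients seen every two days these should be common. Under 13.0 the adverse event count would partly reflect disease persistence and number of visits, and could obscure events caused by the spray.

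The scale is 9 to 21 vital-sign readings per patient, for stopping at Day 6 or Day 14. The number classified differently is unknown. The rates in the working are assumptions and show scale only. The primary outcome, duration of infection by PCR, is unaffected. This is a contradictory recording rule that should be corrected, not a threat to the main efficacy result.

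**What to change.** Before unblinding, reconcile 13.0 with 19.1 to 19.3 so that 13.0 refers to one adverse event definition, based on onset or worsening after the first dose. The text should:

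- define *aberrant* and *significant*;
- state how values abnormal at baseline, values expected from the infection, and a positive qPCR result are classified;
- keep all other out-of-range values as listed vital-sign data;
- add to 18.2 a summary of adverse events by arm, as patients with at least one event under that definition. Showing the number of follow-up visits alongside would help, because Step 4 shows that even this measure varies with follow-up.

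The cost is a cross-reference in 13.0 and a few clarifying sentences in section 19 and 18.2, with no new data. The downside is that fewer readings carry the adverse event label, but none are lost. Settling this before unblinding matters because a definition chosen afterwards would be open to bias.
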